POST-APPROVAL STUDY of TRANSCAROTID ARTERY
REVASCULARIZATION in PATIENTS with SIGNIFICANT CAROTID
ARTERY DISEASE.

The ROADSTER 2 Study

Clinical Protocol	SRM-2015-02
Version	E
Version Date	February 10, 2017

NCT02536378

Sponsored by:

Silk Road Medical, Inc.
[name]
[name]
United States of America
[contact]
[contact]

1 Protocol Summary

Title	POST-APPROVAL STUDY of TRANSCAROTID ARTERY REVASCULARIZATION in PATIENTS with SIGNIFICANT CAROTID ARTERY DISEASE. (The ROADSTER 2 Study)
Objective	The ROADSTER 2 Study is intended to evaluate real world usage of the ENROUTE Transcarotid Stent when used with the ENROUTE Transcarotid Neuroprotection System by physicians of varying levels of training and previous experience with the transcarotid technique.
Study Design	The ROADSTER 2 Study is an open label, single arm, multi-center post-approval Study for the treatment of patients at high risk for adverse events from carotid endarterectomy who require carotid revascularization and who are eligible for treatment with a combination of the ENROUTE Transcarotid Stent System and the ENROUTE Transcarotid NPS.
Enrollment	A minimum of 600 patients treated per protocol. Enrollment will be an entirely new cohort of patients. Additional follow-up on subjects from the ROADSTER IDE will not be included. A maximum of 30 patients per physician will be included in the first 600 patients. A physician may enroll more than 30 patients.
Investigation Site Locations	A minimum of 30 and up to a maximum of 100 sites in the United States. A maximum of 5 sites in the European Union. No more than 30% of the sites will be sites that previously enrolled in the ROADSTER study.
Primary Endpoint	The rate of procedural success through 30 days following stent implant.
Secondary Endpoints	The following secondary endpoints will be assessed 0 to 30 days: 
 ▪ Acute device success ▪ Technical success ▪ Rate of cranial nerve injury ▪ Rate of cardiac death ▪ Rate of neurological death ▪ Rate of hierarchical ipsilateral stroke, death and MI ▪ Rate of hierarchical ipsilateral stroke, death and MI by symptom status ▪ Acute device, technical and procedural success by physician experience ▪ Acute device, technical and procedural success by physician training level ▪ Acute device, technical and procedural success by enrollment quartile
Patient Population	Patients with atherosclerotic extracranial internal carotid stenosis (ICA) with or without involvement of the contiguous common artery (CCA) determined by duplex ultrasound, CT/CTA, MR/MRA or angiography to be: Symptomatic ($\geq 50\%$ stenosis) or Asymptomatic ($\geq 80\%$ stenosis)
Planned Schedule	Commence Enrollment: Q3 2015 Complete Enrollment: End of Q1 2018 Complete 30-day Follow-Up: 30 days following last enrollment Issue FDA Final Report: Beginning of Q3 2018

15 Adjudication of Events

15.1 Clinical Events Committee (CEC)

An independent Clinical Events Committee will be assembled to review and adjudicate strokes, cranial nerve injuries, and UADEs (and their relationship to the device or procedure) events, as well as major protocol deviations affecting patient safety, that occur while a patient is enrolled in the study. The committee will be comprised of a multidisciplinary group of physicians including at least one neurologist, at least one vascular surgeon and at least one cardiologist. The committee members will not be participating in the trial and will not have an affiliation with the Sponsor, Investigators, or Study sites.

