15.2 Strokes

The CEC will adjudicate all suspected strokes.

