15.3 Cranial Nerve Injuries

The CEC will adjudicate all suspected cranial nerve injuries that occur within 30 days (+7 days) of the procedure.

16 Statistical Methods and Determination of Sample Size

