16.1 Overview

The following section provides an outline of the statistical methods to be applied to the clinical data from this study. A Statistical Analysis Plan, containing the details for generating the analyses, will be finalized prior to any analyses being conducted.

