16.2.3 Secondary Endpoint

The analyses to be conducted on the secondary endpoints are intended to provide additional supportive evidence of the efficacy and safety of the device. There are 10 secondary endpoints that will be assessed at 30 days post-procedure; each of the secondary endpoints is a dichotomous variable:

- Acute device success
- Technical success
- Rate of cranial nerve injury

- Rate of cardiac death
- Rate of neurological death
- Rate of hierarchical ipsilateral stroke, death and MI
- Rate of hierarchical ipsilateral stroke, death and MI by symptom status
- Acute device, technical and procedural success by physician experience
- Acute device, technical and procedural success by physician training level
- Acute device, technical and procedural success by enrollment quartile

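### The CEC remit in 15.1 does not list MI or cause of death, so the two cause-specific death rates and the MI part of the composite have no stated independent review

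*Combined protocol and SAP*

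**What the plan says.** The section titled "15 Adjudication of Events" sets out what the committee reviews. Section 15.1 lists "strokes, cranial nerve injuries, and UADEs (and their relationship to the device or procedure) events, as well as major protocol deviations affecting patient safety". It also requires the members to be independent of the sponsor, investigators and sites, and to include at least one neurologist, one vascular surgeon and one cardiologist.

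Two subsections give event-specific detail:

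- 15.2: "The CEC will adjudicate all suspected strokes", followed by definitions of major and minor stroke.
- 15.3: "The CEC will adjudicate all suspected cranial nerve injuries that occur within 30 days (+7 days) of the procedure".

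Section 16.2.3 lists ten secondary endpoints, described as supportive. Three of the entries are "Rate of cardiac death", "Rate of neurological death" and "Rate of hierarchical ipsilateral stroke, death and MI"; a fourth repeats the composite by symptom status. The Protocol Summary places all secondary endpoints in a 0 to 30 day window and describes the study as open label and single arm.

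Section 16.1 defers analysis detail: "A Statistical Analysis Plan, containing the details for generating the analyses, will be finalized prior to any analyses being conducted".

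**The concern.** Four listed endpoints depend on a judgement that the stated remit does not give to the independent committee. Cardiac and neurological death need a cause for each death. The composite needs a decision on whether a suspected MI was one. Stroke and cranial nerve injury, which also feed secondary endpoints, do receive independent review, and nothing in the text seen explains the difference. A cardiologist is required on the committee, but no cardiac event type is assigned to it.

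Treatment is known to everyone at the site, and there is no control arm in which similar classification errors could offset. Followed as written, the composite would combine adjudicated strokes with MIs that have no stated independent review, and the two cause-specific death rates would rest on attribution with no stated independent review. What is at stake is the credibility of a few supportive safety rates that are likely to be based on small counts.

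**Working it through.** **The plan's own figure.** The documents give no expected MI or death rate. The design figure in 16.1.1, the exact lower limit for 534/600, reproduces: Clopper–Pearson gives 86.22% to 91.39%. This point does not touch it.

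**Remit against endpoints**

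| Item needed in 16.2.3 | Stated CEC route in section 15 |
|---|---|
| Stroke part of the composite | Yes, all suspected strokes |
| Death part of the composite | No cause is needed |
| MI part of the composite | None, unless the MI is also a UADE |
| Cardiac death | None, unless the death is also a UADE |
| Neurological death | A fatal suspected stroke is reviewed as a stroke; nothing says the CEC assigns a cause of death |

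The gap is therefore cause-of-death attribution and the MI component.

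**Size.** From the plan: n = 600. All other inputs are assumptions:

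- deaths in 0.5–2% (3–12 patients);
- MI in 0.5–2% (3–12 patients);
- 70–100% of MIs isolated, that is, in patients without ipsilateral stroke or death. On the usual reading of a hierarchical composite, only these change the rate;
- 10–30% misclassified, all in one direction.

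*Cause-specific death* (shift = deaths × error share / 600, with all deaths exposed because no assignment of cause is stated even after a stroke):

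- low: 3 × 0.10 = 0.3 events, or 0.05 points
- high: 12 × 0.30 = 3.6 events, or 0.60 points
- one reattributed death: 1/600 = 0.17 points

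*Composite* (shift = MIs × isolated share × error share / 600):

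- low: 3 × 0.7 × 0.10 = 0.21 events, or 0.035 (about 0.04) points
- high: 12 × 1.0 × 0.30 = 3.6 events, or 0.60 points

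Both shifts are zero if errors balance.

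*By symptom status* (assuming 25–50% symptomatic), one isolated MI moves the symptomatic rate by 1/300 to 1/150 = 0.33–0.67 points and the asymptomatic rate by 1/450 to 1/300 = 0.22–0.33 points.

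**Comparison with sampling error** (Clopper–Pearson, n = 600)

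| Events | Rate | 95% CI | Distance to lower / upper limit (points) |
|---|---|---|---|
| 3 | 0.50% | 0.10–1.45% | 0.40 / 0.95 |
| 4 | 0.67% | 0.18–1.70% | 0.48 / 1.03 |
| 6 | 1.00% | 0.37–2.16% | 0.63 / 1.16 |
| 12 | 2.00% | 1.04–3.47% | 0.96 / 1.47 |
| 24 | 4.00% | 2.58–5.89% | 1.42 / 1.89 |

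For a composite of 2% or 4%, the largest shift (0.60) is below the nearest limit (0.96). For a cause-specific rate, 0.60 is below the distance to the upper limit, which matters most for safety, at every count shown. At 3 or 4 events the lower limit is closer than 0.60, so the extreme case of over-attribution could pass it. That needs 12 deaths, 30% of causes wrong and every error in the same direction. These intervals do not include misclassification.

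**Timing of a change.** Assume even accrual to 31 March 2018 from a start on 1 July or 30 September 2015. The elapsed share at the Version E date (10 February 2017) is 590/1004 = 58.8% or 499/913 = 54.7%. Six months later it is 771/1004 = 76.8% or 680/913 = 74.5%.

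**The case against.** The strongest objection is that this is a claim of absence about a document seen only in part. The text available runs from section 1 to section 15 onward, and the SAP named in 16.1 is separate. Sections 2–14 may well define MI and cause of death and say who classifies them. This stands: the finding is that section 15 does not state a route, not that the plan has none. If a route exists, only a cross-reference is needed.

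A second objection is that a sponsor may choose a limited remit for a post-approval study, and that nothing in 16.2.3 promises adjudicated deaths or MIs. That also stands. A reader might infer that the protocol contradicts itself; it does not. It is a gap in scope.

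Third, no decision is shown to change. The affected endpoints are supportive, with no stated threshold, every rate used above is assumed, and the upper figures need all errors to run one way. This is correct and limits the weight of the point.

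Fourth, the remedy is imperfect. An MI that the site never suspects is still missed, and retrospective review may fail for lack of records. The revised rates could then mix adjudicated and site-classified events. That is why the fix asks for a count of the latter.

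It might also be said that the UADE category covers these events. It does so only for deaths and MIs that qualify as UADEs, which is not review of all of them.

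**Conclusion.** The point holds as a minor, inexpensive improvement. As section 15 is written, cause of death and MI have no stated independent review unless the event is also a UADE, while four secondary endpoints in 16.2.3 depend on them. The largest plausible shift is about 0.6 percentage points for either kind of rate. It could be zero, and it is generally smaller than sampling error. These sizes rest wholly on the assumed event and error rates.

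Two stronger readings are not supported. One is that the composite as a whole lacks adjudication: its strokes are adjudicated and its deaths need no cause. The other is that the primary endpoint is compromised: the definition of procedural success is not in the text seen, so no effect on it can be shown. Confidence is medium because of the sections not seen.

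**What to change.** In 15.1, add to the CEC remit all suspected MIs and all deaths in the 0–30 day window, with cause classed as cardiac, neurological or other. Include events that have already occurred where source records allow. In 16.2.3, state that cardiac death, neurological death and both composite endpoints use CEC-adjudicated events, and report how many events stayed site-classified. If another section or the SAP already assigns independent classification, cross-reference it in 15.1 instead.

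The cost is wording in two sections and in the CEC charter, plus event packets: at the assumed rates, 3 + 3 = 6 to 12 + 12 = 24. Between the Version E date and six months later, about 55–77% of them would be retrospective under even accrual (6 × 0.547 = 3.3 to 24 × 0.768 = 18.4 packets). Section 17 does not show whether the source records needed for these were collected. The required specialties are already on the committee, no patient procedures are added, and the sample size and primary analysis do not change.

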16.2.1 Primary Endpoint

The primary endpoint for the study is the rate of procedural success through 30 days following stent implant. The derivation of the endpoint for the primary analysis of the primary endpoint will consider all patients who undergo the procedure and in the absence of a major protocol deviation, i.e., the Per Protocol population. Patients who exit the study prior to the 30 day post-procedure evaluation who meet the definition of a procedural success based on their last observation will be counted in the analysis as a procedural success. Secondary analyses of the primary endpoint will consider alternative methods of imputation; the details of these supplemental analyses will be described in the Statistical Analysis Plan.

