16.4 Populations for Analysis

The Per-Protocol population is defined as patients who sign an informed consent, undergo the study procedure, independent of the success of the procedure, and with the absence of major protocol deviations. Patients who sign an informed consent, however fail to undergo the study procedure, will not be included in the Per-Protocol population. A maximum of 30 patients treated per protocol per physician can contribute to the 600 patient minimum. A physician may enroll more than 30 patients.

The primary endpoint and all secondary endpoints will be analyzed based on the Per-protocol population. All available data on the Per-Protocol patients who enrolled in the study will be included. Any subject not meeting the Inclusion/Exclusion criteria will be tabulated but not included in the primary endpoint analysis.

17 Data Collection

Data will be entered into a validated electronic data management system. Data fields in the selected electronic data management system used will be aligned such that it overlaps with the appropriate data fields for the post-approval study as derived from the ROADSTER IDE.

18 Sponsor Responsibilities

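### Exclusion from the Per-Protocol population for a major deviation is not required to be blind to outcome, so failures can be removed selectively from the primary test

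*Combined protocol and SAP*

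**What the plan says.** Section 15.1 sets up a committee whose members "will not have an affiliation with the Sponsor, Investigators, or Study sites". Its remit covers the outcome events (strokes, cranial nerve injuries, unanticipated adverse device effects) "as well as major protocol deviations affecting patient safety, that occur while a patient is enrolled in the study". Section 15.2 adds: "The CEC will adjudicate all suspected strokes".

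Section 16.4 admits to the Per-Protocol population consented patients who "undergo the study procedure, independent of the success of the procedure, and with the absence of major protocol deviations". Section 16.2.1 agrees: the primary analysis "will consider all patients who undergo the procedure and in the absence of a major protocol deviation, i.e., the Per Protocol population". Section 16.4 also states: "The primary endpoint and all secondary endpoints will be analyzed based on the Per-protocol population". The minimum of 600 is counted on patients treated per protocol (section 1, Enrollment, and section 16.4).

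The only alternative analyses promised for the primary endpoint concern missing data: "Secondary analyses of the primary endpoint will consider alternative methods of imputation". No second analysis population is named. Section 1 describes an "open label, single arm, multi-center post-approval Study".

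The available text does not define a major deviation, does not say who assigns that label or when, and does not blind the assignment to outcome. Sections 2 to 14 are not part of the available text, so some of this may be settled there.

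**The concern.** The primary test depends on who is left out of the Per-Protocol population, and the text leaves open whether that decision is taken with the outcome in view.

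Take two treated patients with the same intra- or post-procedural deviation. If one has a suspected stroke, the case goes to the committee under section 15.2, and the deviation is more likely to be noticed and judged to be major. If the other has an uneventful course, nothing in sections 15 or 16 prompts an equivalent search. This difference in detection is a plausible inference; the documents do not describe how deviations are found. If it occurs, exclusions fall more heavily on failures than on successes, and the observed success rate rises with no change in performance.

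Two features of the design make this harder to see or correct. With a single arm, no control group would show differential exclusion. With 600 counted per protocol, an excluded failure does not count towards the minimum and can be replaced by another patient.

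**Working it through.** **Inputs from the documents.** Threshold 85%, two-sided 95% exact binomial interval, planning case 534/600, stated lower limit 86.22% (all section 16.1.1); 600 minimum counted per protocol (sections 1 and 16.4).

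**Inputs assumed.** The number or share of failures excluded, that only failures are excluded, and that a stroke counts as a procedural failure. The available text gives no figure for the first two and no definition for the third.

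**Step 1: reproduce the plan's figure.** The Clopper-Pearson lower limit for x successes in n is the 0.025 quantile of Beta(x, n − x + 1). For 534/600 this is Beta(534, 67), giving 86.22%, as stated.

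**Step 2: the pass mark.** At n = 600 the smallest passing count is 528 (88.0%, lower limit 85.13%); 527 fails (84.95%). At a true 85%, P(X ≥ 528 | 600, 0.85) = 2.0%. At a true 89% the chance of passing is 80.3%.

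**Step 3: add excluded failures back to the planning case.** With k excluded failures, the all-treated result is 534/(600 + k).

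| k | All treated | Rate | Lower limit |
|---|---|---|---|
| 0 | 534/600 | 89.0% | 86.22% |
| 5 | 534/605 | 88.3% | 85.43% |
| 8 | 534/608 | 87.8% | 84.96% |
| 10 | 534/610 | 87.5% | 84.66% |
| 20 | 534/620 | 86.1% | 83.16% |

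The smallest k that takes the lower limit below 85% is 8. That is 8/608 = 1.3% of treated patients, or 8 of 66 + 8 = 74 failures.

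**Step 4: effect on the false-positive rate.** Let true all-treated success be 85% and let a share f of failures be excluded. The success rate among those retained is p = 0.85/(0.85 + 0.15(1 − f)). With 600 per protocol, the chance of passing is P(X ≥ 528 | 600, p).

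| f | p | Share of treated excluded (0.15f) | Chance of passing |
|---|---|---|---|
| 0 | 85.0% | 0% | 2.0% |
| 5% | 85.6% | 0.75% | 5.3% |
| 10% | 86.3% | 1.5% | 12.3% |

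**The case against.** **The committee's ruling is not stated to decide Per-Protocol membership.** This is correct. A reader might infer from section 15.1 that the committee decides who is excluded, but no section says so. The committee is only the one body that the available text names as adjudicating any major deviations, and the link to the analysis population is left open.

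**The safety clause does not define a major deviation.** This also stands. In section 15.1 the clause selects which major deviations go to the committee, and it may refer to potential harm. Under section 16.4 every major deviation excludes, so as written the event-free patient with the same major deviation should leave too. The unequal treatment arises only if detection or classification differs by outcome. The text neither describes nor prevents that.

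**A bad outcome alone cannot exclude a patient.** A reader might infer that a stroke by itself triggers exclusion. It does not: a deviation must exist, and section 16.4 keeps patients regardless of procedural success. But that wording only says that failure is not an exclusion criterion. It does not stop knowledge of failure from influencing who is found to have a major deviation.

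**The committee is independent, and the SAP is to be finalised before any analysis.** Independence limits conflict of interest, but it does not remove hindsight or unequal detection. Finalising the SAP before analysis (section 16.1) does not blind case-by-case classification in an open-label study.

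**The verdict may rarely turn on this.** Section 16.1.1 cites earlier success rates of 91.0% and 95.7%. At a true 91% a 600-patient test passes about 99% of the time without any exclusion. That is fair, and the failures-only scenario is the extreme case. But the planning case is 89%, because section 16.1.1 expects outcomes from early enrolment at new sites to count, and there 8 patients matter.

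**Conclusion.** The concern holds as a gap in safeguards. Sections 15.1, 16.2.1 and 16.4 together permit outcome-dependent exclusion from the only population named for the primary endpoint, and nothing in the available text prevents it. They do not show that such exclusion is intended or that it occurred.

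The size is conditional. Eight selectively excluded failures are enough to separate a Per-Protocol pass at the planning case from an all-treated lower limit below the threshold. Excluding 5% to 10% of failures raises the false-positive rate to roughly two and a half to six times its nominal 2.0% (5.3/2.0 and 12.3/2.0). Exclusions spread evenly over successes and failures would not have this effect.

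The conclusion rests on the assumptions listed in the working and on sections 2 to 14 containing no rule for outcome-blind classification. A definition of major deviations in those sections would narrow the point, but would not by itself equalise detection. The point merits a change to the plan, with medium confidence.

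**What to change.** In sections 15.1 and 16.4, and in the SAP:

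- Apply a prespecified list of major deviations to every treated patient, from case report form data, without access to post-procedure outcomes.
- Lock the Per-Protocol flag before it is linked to adjudicated events.
- State that a committee finding that a deviation affected safety is reported as a safety finding and does not by itself set or change the flag.
- Report the primary endpoint in all treated patients beside the Per-Protocol result, and list each exclusion by reason and outcome. This makes selective exclusion visible, but it does not replace the first three steps, because the primary test stays on the Per-Protocol population.

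The cost is wording in the protocol, the SAP and the committee's charter, one reordered review step, one further table and one listing. The reported success rate may be slightly less favourable.
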